### **Safety Analysis**

This study is not designed to compare safety between study arms using inferential statistics. However, we do intend to report on safety of the amoxicillin challenge. Safety endpoints will be presented for the safety analysis set in tabular form using counts and proportions.

We will also report safety events observed from penicillin treatments grouped by whether the participant was randomized to intervention, and whether they received full active intervention or not. Statistical testing is not expected; differences in event rates between groups will be computed with 95% confidence intervals.

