### **Safety endpoints**

The key safety endpoints for this trial are potentially associated adverse events with the amoxicillin challenge, these are prespecified as:

- Anaphylaxis
- Other potentially allergic symptoms during/after amoxicillin challenge- e.g. rash
- Nausea/Vomiting/GI symptoms only
- Other symptoms during amoxicillin challenge

For reactions to penicillin given during the hospital stay, the same events will be captured:

- Anaphylaxis
- Other potentially allergic symptoms during/after penicillin administration- e.g. rash
- Nausea/Vomiting/GI symptoms only
- Other symptoms during penicillin administration

Due to the nature and clinical course of patients receiving routine hospital care, a substantial number of adverse events are expected among participants, including but not limited to:

- Death
- Sepsis
- Renal failure

- Respiratory failure
- Heart failure
- Pneumonia or other / new infection
- DVT or PE
- Complications related to ICU procedures
- Arrhythmia
- Delirium
- Bowel ischemia
- Ileus
- Leukopenia or leukocytosis
- Anemia or thrombocytopenia
- Coagulopathy (DIC)
- Hypoglycemia
- Electrolyte abnormalities

These adverse events are common in hospitalized patients and are thus not expected to reflect safety of the treatment regimen. There is no plan to summarize or report these events.

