### **Safety analysis set**

Participants who received a dose of amoxicillin as a challenge will be included in the safety analysis set related to the safety of the intervention. All other participants will be classified as not having received an intervention with oral challenge to disprove their allergy label, and thus there are no adverse events potentially associated with the control group.

In addition to reporting the safety of the challenge itself, we also intend to compare the incidence of safety events from use of penicillin between the two groups. This analysis will include the intent-to-treat analysis set.

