#### Reporting of Safety Events:

- Adverse events associated with amoxicillin challenge
  - as n (proportion) of total challenges
- Adverse events associated with same hospitalization use of a penicillin antibiotic
  - as n (proportion of total PALs)

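### The planned between-arm safety difference covers reactions to penicillin treatment only, so no planned contrast gives total penicillin-class reactions per labelled patient by arm

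*SAP*

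**What the plan says.** The SAP handles penicillin-class reactions in two streams.

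- **Challenge dose.** Under Safety analysis set (SAP 9): "Participants who received a dose of amoxicillin as a challenge will be included in the safety analysis set related to the safety of the intervention". Everyone else is treated as not having had a challenge, "thus there are no adverse events potentially associated with the control group". The Safety Analysis section (SAP 10) presents this set as counts and proportions, and Reporting of Safety Events uses total challenges as the denominator.
- **Penicillin given as treatment.** The same SAP 9 section adds that "we also intend to compare the incidence of safety events from use of penicillin between the two groups", and continues: "This analysis will include the intent-to-treat analysis set". The Safety Analysis section repeats this: "We will also report safety events observed from penicillin treatments grouped by whether the participant was randomized to intervention". It also groups by whether the full active intervention was received, and promises differences in event rates with 95% confidence intervals but no expected testing. Reporting of Safety Events lists "Adverse events associated with same hospitalization use of a penicillin antibiotic", with total labelled patients as the denominator.

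Safety endpoints (SAP 3) keeps the same separation. It lists challenge events first and then says: "For reactions to penicillin given during the hospital stay, the same events will be captured". No section defines an outcome that combines the two streams by arm.

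**The concern.** Protocol 2.0 aims to establish the safety of the single-dose challenge as a strategy. For a strategy compared by arm, the natural question is how many labelled patients had any penicillin-class reaction under each policy. The planned difference answers a narrower question, because an intervention patient who reacts to the challenge dose contributes no event to it. A treatment-only difference near zero, or slightly in favour of the intervention, could therefore be read as showing no net harm when the total is higher in the intervention arm.

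Two smaller matters are tied to this. First, the SAP never says outright whether the challenge dose counts as penicillin use. Amoxicillin is on its penicillin list (Key secondary endpoints, antibiotic utilization), SAP 9 speaks of use, and the Safety Analysis speaks of treatments. The separate lists imply that the challenge is excluded, but two programmers could build different contrasts. Second, the statement that the control group has no associated events does not fit the rest of the documents.

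**Working it through.** The documents give no safety event rate, margin or safety power, so there is no plan figure to reproduce. The check compares the passages and then sizes the omitted component.

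**1. Control challenges.** SAP 9 presumes no associated events in controls. Protocol 5.0 (Control Arm) includes direct amoxicillin challenge at the primary team's discretion in usual care. Protocol 8.0 plans to count challenges in both arms. SAP 8 (Power and Sample Size) assumes that 0.5% of control patients have a label removed or a test-dose challenge. The safety set is also defined by dose received, not by arm. These passages conflict.

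**2. What the treatment-only difference leaves out.** Count each labelled patient once. Then

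total difference = treatment-only difference + (challenge-only reactors, intervention − challenge-only reactors, control),

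with each term a proportion of labelled patients and challenge-only meaning a reaction to the challenge but none to treatment. If the bracket is positive, the treatment-only difference understates the total. It has the opposite sign when it is negative but smaller in size than the bracket.

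**3. Illustrative size.** Inputs:

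- 12 units, one-month steps, 10–15 labelled patients per unit per month (SAP 8).
- Assumption: one unit crosses over each month and the first is live in month 1. Intervention unit-months = 1 + 2 + … + 12 = 78, and control unit-months = 144 − 78 = 66.
- Labelled patients: intervention 78 × 10 to 78 × 15 = 780–1,170; control 66 × 10 to 66 × 15 = 660–990.
- Assumption: 10% or 20% of intervention patients are challenged. The plan gives no challenge rate. These are its label-removal figures in SAP 8, used as a stand-in.
- Assumption: reaction rate per challenge of 1% or 3.6%. The first comes from the alert text in Protocol 5.0 (under 1% likely to have a positive skin test). The second is 100% − 96.4%, from the lower limit of the tool's predictive-value interval. Neither is a measured reaction rate to one challenge dose.

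Events omitted = labelled patients × share challenged × reaction rate. Points omitted = share challenged × reaction rate.

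| Share challenged | Challenges | Events at 1% | Points at 1% | Events at 3.6% | Points at 3.6% |
|---|---|---|---|---|---|
| 10% | 78–117 | 0.8–1.2 | 0.10 | 2.8–4.2 | 0.36 |
| 20% | 156–234 | 1.6–2.3 | 0.20 | 5.6–8.4 | 0.72 |

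At the upper limit of the predictive-value interval (0.1% allergic), the omission is only 0.08–0.23 events.

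**4. Control side.** If the whole 0.5% were challenges, 0.005 × 660 to 0.005 × 990 = 3.3–5.0 control patients would be challenged. At 3.6% that is at most 5.0 × 0.036 = 0.18 events. The contradiction in step 1 is real but numerically small.

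**5. Scale.** If 0.5% per arm reacted to treatment (an assumption), the 95% half-width ignoring clustering is 1.96 × √[0.005 × 0.995 × (1/780 + 1/660)] = 0.73 points, or 0.60 points with 1,170 and 990. The omission is well inside the interval at 1%. It is about the size of the interval's half-width only at 3.6% with 20% challenged.

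**The case against.** The strongest reply is that challenge harm is not hidden. It is a safety endpoint by category, a key secondary endpoint with time windows, and tabulated per challenge. The Main Analysis section also gives challenge response per total labelled patients. With few control challenges, a reader could come close to the total by adding the tables. The Safety Analysis also says the study is not designed for inferential safety comparison, and its grouping by full intervention received already shows part of the conditioning. All of this stands, and it limits the point to one missing descriptive contrast. Adding tables still gives no confidence interval and does not count each patient once. The general rule for secondary endpoints, which compares binary outcomes by adjusted logistic regression, helps only nominally, because tolerance and challenge events are defined only in challenged patients.

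Four stronger readings are tempting but not supported:

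- *The harm caused by the intervention is absent from the arm contrast.* Reactions to same-stay penicillin given after label removal are also caused by the intervention, and they are in the contrast. Only the direct challenge component is outside.
- *The challenge table is one-arm by definition.* It is defined by dose received, and controls may be challenged.
- *Reactors systematically leave the treated stream, while a control patient's first exposure is normally treatment.* This is plausible, but no section says it. Usual care is described as doing nothing or working around the label.
- *A large fixed share of intervention-arm reactions is omitted*, calculated from the shares challenged and treated. That needs equal risk per exposure, which challenging only low-risk patients contradicts, and a treatment share the documents do not give.

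A fair point about the remedy also stands. Challenges have scheduled vital signs (Protocol 5.0) and smart-phrase documentation (SAP 3), and nothing equivalent is described for treatment reactions. A combined count would therefore mix different levels of ascertainment.

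**Conclusion.** The point holds in this form: the between-arm difference covers treatment reactions only, challenge reactions are reported only among the challenged, and no planned contrast gives the total per labelled patient by arm. The SAP's no-events premise for controls must be reconciled with the passages that allow control challenges.

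The likely size is modest: about 1–2 events (0.1–0.2 points) at 1% reacting and about 3–8 events (0.36–0.72 points) at 3.6%. This rests on the assumed 78 intervention unit-months, on 10–20% challenged, and on reaction rates borrowed from the alert and the predictive-value interval. Those rates concern allergy only, so gastrointestinal and other symptoms, which the SAP also counts, could add to the total. The change is worth making because it affects what the trial can say about net harm and costs little.

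**What to change.** 1. In SAP 9 (Safety analysis set) and SAP 10 (Safety Analysis), state that the challenge dose is not counted as penicillin treatment, and label the treatment-only difference as excluding challenge reactions.
2. Reconcile the SAP 9 statement about control events with Protocol 5.0, Protocol 8.0 and SAP 8.
3. Keep both existing tables, and show challenge events by arm.
4. Add one descriptive intent-to-treat row by arm: labelled patients with any reaction to any penicillin-class dose in the index stay, challenge included, each patient counted once. Show it by category, with anaphylaxis and other allergic reactions separate from gastrointestinal-only and other symptoms, and give the difference with a 95% confidence interval. It supplements the component tables and does not replace them.
5. Footnote the row to say that challenges are observed and documented more closely than treatment doses.

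The cost is a few sentences and one row from data already planned for collection. The intervention arm's reported rate becomes slightly less favourable, and closer observation around challenges may raise its count further, which is why the footnote is needed.

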## 1. INTRODUCTION

This document describes the statistical analysis plan (SAP) for a single center, stepped wedge, randomized, pragmatic, clinical trial of an intervention to remove low risk penicillin allergy labels using a single dose amoxicillin challenge. The intervention is deployed at the medical unit level, led by a unit pharmacist. Persons on the unit with a penicillin allergy label undergo a risk assessment, and low risk patients who consent to the procedure are presented with an oral amoxicillin challenge.

At the study outset, all participating units were naïve to the process for removing penicillin allergies. After the run-in period, medical units transitioned from the control condition to the intervention condition at monthly intervals. Medical units at VUMC will be randomized to determine the order in which they start the intervention.

This SAP describes the approach to analyzing the primary and secondary endpoints, as well as safety endpoints, once the trial is stopped.

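### The SAP's by-receipt comparison of penicillin reactions is confounded by selection on allergy risk; differences with 95% intervals should be limited to intervention versus control

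*SAP*

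**What the plan says.** Two places in the SAP deal with reactions to penicillin given as treatment, as distinct from reactions to the challenge dose.

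- **Section 9, Safety analysis set.** The SAP says "we also intend to compare the incidence of safety events from use of penicillin between the two groups", and adds "This analysis will include the intent-to-treat analysis set". This is a comparison of intervention with control.
- **Section 10, Safety Analysis.** The same events are reported "grouped by whether the participant was randomized to intervention, and whether they received full active intervention or not". The next sentence reads "Statistical testing is not expected; differences in event rates between groups will be computed with 95% confidence intervals". No adjustment, restriction or low-risk comparator is given. The subsection opens with "This study is not designed to compare safety between study arms using inferential statistics".

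The SAP does not define full active intervention. Section 2 describes the intervention as identifying labelled patients, applying the risk tool, and using a challenge order set for those who come out as low risk. Section 1 says that "low risk patients who consent to the procedure are presented with an oral amoxicillin challenge".

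The listed denominator for adverse events with same-hospitalisation penicillin is the total number of penicillin allergy labels (section 10, Main Analysis and Reporting of Safety Events). It is not the number of patients given penicillin.

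**The concern.** Assignment in this trial follows unit and date. Receipt does not: it follows the risk tool's result, the patient's consent and whether staff reached the patient. If receipt includes the challenge, recipients were selected for a low predicted chance of penicillin allergy, which is the main driver of the outcome being compared. Non-recipients are a mixture of higher-risk patients, low-risk patients who declined, and patients never assessed.

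An unadjusted difference between such groups would not be zero in general, even if the intervention had no effect on reactions. Leaving out a p-value does not help, because a difference with a 95% interval will be read as an effect estimate. The protocol (section 2.0) names safety among its aims, so a table of this kind could be cited as evidence on that aim.

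**Working it through.** The Safety Analysis subsection states no numerical result, so there is no figure to reproduce. The check is how large a by-receipt difference selection alone can produce.

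**Inputs from the documents**
- Allergy among all labelled patients: 4% or less (Protocol 1.0). Used as an upper value: 4%.
- Allergy among patients classed as low risk: under 1% (alert text, Protocol 5.0). The negative predictive value is >99%, 95% CI 96.4 to 99.9 (Protocol 5.0; SAP section 2). Used as an upper value: 1%. At the lower confidence limit: 100 - 96.4 = 3.6%.

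**Assumptions (not in the documents)**
- Share of labelled patients who are low risk, s: 30% to 70%.
- Share of those who receive the full intervention, c: 20% to 80%.
- Full receipt includes the challenge, so recipients are a fraction f = s × c of labelled patients.
- The intervention has no effect on reactions, the reaction risk equals the probability of true allergy, and within each group penicillin is given without regard to that probability.

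**Per patient given penicillin**

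The overall risk is a mixture of recipients and non-recipients, so

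risk in non-recipients = (4% - f × 1%) / (1 - f).

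| s | c | f | Recipients | Non-recipients | Difference (points) |
|---|---|---|---|---|---|
| 0.3 | 0.2 | 0.06 | 1.0% | 3.94/0.94 = 4.2% | -3.2 |
| 0.5 | 0.5 | 0.25 | 1.0% | 3.75/0.75 = 5.0% | -4.0 |
| 0.7 | 0.8 | 0.56 | 1.0% | 3.44/0.44 = 7.8% | -6.8 |

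**Same calculation at the tool's lower confidence limit (3.6% in low-risk patients)**
- f = 0.06: (4 - 0.216)/0.94 = 4.0%, a gap of 0.4 points.
- f = 0.56: (4 - 2.016)/0.44 = 4.5%, a gap of 0.9 points.

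The gap therefore depends heavily on how well the tool separates risk.

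**Per labelled patient (the SAP's listed denominator)**

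The rate is the share given penicillin times the risk per patient given it. In the middle case (1% versus 5%), with assumed shares given penicillin:

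| Use, recipients | Use, non-recipients | Rate, recipients | Rate, non-recipients |
|---|---|---|---|
| 30% | 30% | 0.30% | 1.50% |
| 30% | 10% | 0.30% | 0.50% |
| 30% | 5% | 0.30% | 0.25% |

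The sign reverses once recipients' use exceeds non-recipients' use by more than the ratio of the two risks. That ratio is 5 in the middle case, and 4.2 to 7.8 across the range. Label removal is meant to make penicillin usable, so higher use in recipients is plausible. The documents give no figure for it.

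**The case against.** The strongest reply has four parts.

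1. *The comparison by assignment is already planned.* True. Section 9 specifies it, and the grouping in section 10 begins with assignment. A reader might infer that the SAP replaces it with an as-received analysis; it does not. The by-receipt contrast is an addition.
2. *The sentence on differences does not say which groups it covers, and the SAP disclaims inferential safety comparison.* Also true. But it directly follows a sentence that sets up groups by receipt, and nothing exempts them. The disclaimer is at odds with printing the interval.
3. *Full active intervention might mean only that the risk assessment was completed.* Recipients would then include higher-risk patients, and the selection would be weaker. The text does not exclude this. The challenge order set is listed as part of the intervention, so including the challenge is the more natural reading, but it remains a reading.
4. *Readers could rebuild the difference from published counts.* They could, but a descriptive label and a breakdown by risk class would show them why it should not be read as an effect.

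Two stronger readings are tempting. One is that the difference must favour the intervention. That holds per patient given penicillin under the assumptions above. It need not hold per total labels, or if clinicians give penicillin to non-recipients only when they judge them low risk. The other takes the gap between low-risk and all other patients as the size of the problem: (4% - s × 1%)/(1 - s) gives 5.3%, 7.0% and 11.0% for s = 0.3, 0.5 and 0.7. Those are risk strata, not receipt groups. Non-recipients also include low-risk patients who declined or were not reached, which dilutes the contrast.

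**Conclusion.** The point holds in a limited form. If full active intervention includes the challenge, the by-receipt difference is confounded by predicted allergy risk and cannot be read as an effect of the intervention. Per patient given penicillin, selection alone could produce about 1% versus 4.2-7.8%. This takes the documents' 4% and 1% as upper values and rests on assumed low-risk shares and uptake. The gap falls to 0.4-0.9 points at the lower confidence limit of the tool's negative predictive value. With total labels as denominator, neither size nor direction can be stated in advance.

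This is a minor secondary safety matter. The primary analysis is unaffected, and the planned comparison of intervention with control does not carry this selection on receipt.

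**What to change.** In SAP section 10, Safety Analysis:

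- Limit rate differences and 95% intervals to intervention versus control in the intent-to-treat set, as section 9 already plans.
- Show the by-receipt breakdown as counts by risk class (low, higher, highest, not assessed), giving both the number given penicillin and the total labels. Label it descriptive and non-causal, with no difference or interval.
- Define full active intervention in the same sentence, stating whether it requires the challenge or only a completed risk assessment.

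The cost is a short edit to the subsection and the loss of one by-receipt interval. The SAP already plans to describe risk class, challenge receipt and same-hospitalisation penicillin use, so no new data are needed.

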#### Reporting of Safety Events:

- Adverse events associated with amoxicillin challenge
  - as n (proportion) of total challenges
- Adverse events associated with same hospitalization use of a penicillin antibiotic
  - as n (proportion of total PALs)

### **Analysis of secondary endpoints**

We will proceed with exploring the effect of low-risk penicillin allergy challenge on secondary endpoints in a similar manner as for the primary endpoints:

- i) Endpoints will be described as medians and interquartile ranges or frequencies and proportions
- ii) Binary variables will be compared using an adjusted logistic regression, and ordered or continuous variables will be compared using proportional odds logistic regression
- iii) The odds ratios with confidence will be reported as estimates of effect size.
- iv) Secondary endpoints will be modelled with adjustment for baseline covariates; sensitivity analyses will exclude adjustment and may include imputation for any missing outcomes.
- v) Differential treatment effects will be evaluated using the interaction term, and consequent differential effects reported
- vi) Time to return of penicillin allergy labels will be evaluated using a Cox proportional hazards model with covariate adjustment.

## 11. SUMMARY

The analyses described here are those necessary **to answer the trial's primary** question of whether an intervention to actively risk-stratify and challenge low-risk penicillin allergies is more effective at removing these allergies than the standard of care (which is to work around them).

Beyond our analysis exploring the effect of challenge on primary and secondary endpoints, we expect there to be multiple additional exploratory analyses conducted. It is not possible to predetermine the nature of such analyses. However, we are committed to preserving rigor and reproducibility and will pre-specify each subsequent analysis in the context of the specific question to be answered, cognizant of bias and missingness in the data.

